#### **Efficacy Assessments:**

- Response Assessments: Disease activity will be assessed by the study investigators, by using CBC and peripheral blood cell morphological examination, examination of bone marrow aspiration (or biopsy if required), and physical exam. Modifications to the Revised Recommendations of the International Working Group (IWG) for Diagnosis, Standardization of Response Criteria, Treatment Outcomes, and Reporting Standards for Therapeutic Trials in Acute Myeloid Leukemia will be used (Appendix 3). Response assessment will be based on bone marrow aspirate/biopsy and the best CBC up to 14 days post bone marrow aspirate/biopsy. Responses will be categorized as:
  - CR (mCR [morphologic CR], CRc [cytogenetic CR], or CRm [molecular CR]);
  - CRh (CR with partial hematologic recovery);
  - CRi (CR with incomplete blood count recovery): CRn (CR with incomplete neutrophil recovery) or CRp (CR with incomplete platelet recovery);
  - o MLFS;
  - PR;
  - o OB;
  - o SD;
  - o PD.

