# 7.10 Efficacy Assessments

Response Assessments: evidence of clinical activity in these patients will be assessed by the study investigators by using CBC and peripheral blood cell morphological examination, examination of bone marrow aspiration (or biopsy if required), and physical exam according to the rules modified from the Revised Recommendations of the International Working Group

(IWG) for Diagnosis Standardization of Response Criteria, Treatment Outcomes, and Reporting Standards for Therapeutic Trials in Acute Myeloid Leukemia (Appendix 3), with modifications as described below. Response assessment will be based on bone marrow aspirate/biopsy and the best CBC up to 14 days post bone marrow aspirate/biopsy. Responses will be categorized as:

- CR: mCR (morphologic CR), CRc (cytogenic CR), or CRm (molecular CR);
- CRh (CR with partial hematologic recovery);
- CRi (CR with incomplete blood count recovery): CRn (CR with incomplete neutrophil recovery) or CRp (CR with incomplete platelet recovery);
- MLFS (morphologic leukemia free state);
- PR (partial response);
- OB (other benefit);
- SD (stable disease);
- PD (progressive disease).

Bone marrow assessment should be performed at the end of each cycle whenever possible. However, at the end of Cycle 2, and at the end of each subsequent even cycle, in consultation with the Medical Monitor, the bone marrow assessment may be missed if the patient has clearly not achieved CR or CRh using the following criteria:

- The patient has not achieved CR/CRh because the peripheral blood neutrophils are  $< 500/\mu$ L or platelets are  $< 50,000/\mu$ L, based on Study Day 22 CBC results for the cycle in question, and
- The results of the bone marrow assessment will not influence the decision to continue study treatment (i.e., assessment of risks and benefits).

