Progressive disease	NA	NA	NA	
 
Evidence for an increase in bone marrow blast percentage and/or increase of absolute blast counts in the blood:
 
> 50% increase in marrow blasts over baseline (a minimum 15% point increase is required in cases with < 30% blasts at baseline; or persistent marrow blast percentage of > 70% over at least 3 mo; without at least a 100% improvement in ANC to an absolute level (>0.5 x 10^9/L [500/mL], and/or platelet count to >50 x 10^9/L [50 000/mL] non-transfused); or
 
> 50% increase in peripheral blasts (WBC x % blasts) to > 25 x 10^9/L (> 25 000/mL) (in the absence of differentiation syndrome)†; or
 
New extramedullary disease
 
	In general, at least 2 cycles of flotetuzumab should be administered to determine "progressive disease". "Progressive disease" is usually accompanied by a decline in ANC and platelets, increased transfusion requirement, and decline in performance status or increase in symptoms		
Recurrence/relapse	Relapse after CR is defined as a reappearance of leukemic blasts in the peripheral blood and $\geq$ 5% blasts in the bone marrow not attributable to any other cause (e.g., bone marrow regeneration after consolidation therapy)						

CR = complete remission (includes mCR, CRc, CRm).

 $CRi = includes neutrophil count \ge 1000 \text{ or platelet count} \ge 100,000.$ 

\*Assessment is quantitated by BM biopsy and best CBC (up to 14 days post BM biopsy).

# No RBC and/or platelet transfusion within 5 days prior to response assessment.

§ No platelet transfusion within 5 days prior to response assessment

† Certain targeted therapies, for example, those inhibiting mutant IDH proteins, may cause a differentiation syndrome, that is, a transient increase in the percentage of bone marrow blasts and an absolute increase in blood blasts; in the setting of therapy with such compounds, an increase in blasts may not necessarily indicate PD.

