6 STUDY ENDPOINTS

6.1 Primary Efficacy Endpoint

The primary efficacy endpoint for the PIF/ER AML pivotal expansion cohort is the rate of CR/CRh as assessed by the study investigators.

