11 EFFICACY ANALYSES

Disease activity will be assessed by the study investigators by using CBC and peripheral blood cell morphological examination, examination of bone marrow aspiration (or biopsy if required), and physical examination. Modifications to the Revised Recommendations of the International Working Group for Diagnosis (IWG), Standardization of Response Criteria, Treatment Outcomes, and Reporting Standards for Therapeutic Trials in Acute Myeloid Leukemia will be used (**Appendix 1**). Response assessment will be based on bone marrow aspirate/biopsy and the best CBC up to 14 days post bone marrow aspirate/biopsy. Responses will be categorized as:

- CR: mCR (morphologic CR], CRc (cytogenic CR], or CRm (molecular CR);
- CRh (CR with partial hematologic recovery);
- CRi (CR with incomplete blood count recovery): CRn (CR with incomplete neutrophil recovery) or CRp (CR with incomplete platelet recovery);
- MLFS (morphologic leukemia free state);
- PR (partial response);
- OB (other benefit);
- SD (stable disease);
- PD (progressive disease).

The number and percent of PIF/ER AML patients will be summarized by best overall response. Efficacy analyses will be based on the PIF/ER AML population

. All efficacy results will be summarized by PIF, ER and the total combined PIF/ER populations.

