11.1 Primary Efficacy Analysis

The primary efficacy endpoint for the AML expansion cohort is the CR/CRh rate, calculated as the proportion of patients in the efficacy population that has achieved a best response of CR (mCR, CRc, or CRm) or CRh at any point during treatment by investigator's assessment, according to IWG AML response criteria (Appendix 1). CR/CRh rate will be summarized for total combined PIF/ER patients as the primary analysis, as well as for PIF and ER patients, separately, and for PIF/ER patients in the response evaluable population as a sensitivity analysis. A two-sided exact 95% confidence interval will be calculated around response rates.

For the second interim analysis of 100 patients, as well as for the final analysis of 170 patients, all treated patients will be followed for at least 6 months or death from any cause, whichever comes first, prior to data cut off for the analysis. If the trial passes the pre-specified efficacy boundary (25% observed CR/CRh rate) at the second interim analysis, a two-sided exact 95% confidence interval described by Jennison and Turnbull (44) will be produced to account for the bias in the conventional exact confidence interval for fixed sample test.

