11.2.1 Key Secondary Efficacy Analyses

The key secondary efficacy endpoints include CR rate, CRh rate, duration of response, postbaseline transfusion independence rate, HSCT rate and incidence and duration of hospitalization.

Duration of response (DOR) will be calculated from the time of initial documentation of response to the time of disease relapse or death due to any cause, whichever occurs first. Patients who are still in response at study completion without alternative therapies will be censored at the time of their last disease assessment.

Duration of response will be calculated for patients who achieve the first evidence of CR or CRh as primary analysis. A separate exploratory analysis will be conducted for patients who achieve the first evidence of complete response (CR, CRh, CRi [CRn, CRp], or MLFS).

DOR (months) = (date of event [disease relapse or death] or date of censoring –date of first evidence of response + 1) / (365.25/12)

Sensitivity analyses will be done for duration of response by using the additional censoring rules below:

- Censored at the date of HSCT.
- Censored at the date of other alternative therapies such as surgery, procedure, radiation and subsequent antileukemic therapy, etc.
- Patients with two or more consecutive missing response assessments prior to event will be censored at the last date of response assessment before the missing assessments.

The duration of response will be analyzed using the KM method. The 25th percentile, median and 75th percentile time (including two-sided 95% CI) will be summarized.

Post-baseline transfusion independence is defined as no transfusion during any consecutive 56-day period on-study. Post-baseline transfusion independence will be summarized for RBC and platelet transfusion separately and in total. Transfusion dependence at baseline is defined as any red blood cell or platelet transfusions during the 28 days prior to the first dose of study drug. The rate of conversion from transfusion dependence to transfusion independence will be calculated. The rate of patients who are transfusion independent at baseline and remain independent during any 56-day post-baseline period will also be calculated.

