Progressive disease	NA	NA	NA	 Evidence for an increase in bone marrow blast percentage and/or increase of absolute blast counts in the blood: > 50% increase in marrow blasts over baseline (a minimum 15% point increase is required in cases with < 30% blasts at baseline; or persistent marrow blast percentage of > 70% over at least 3 mo; without at least a 100% improvement in ANC to an absolute level (>0.5 x 10%/L [500/mL], and/or platelet count to >50 x 10%/L [50 000/mL] non-transfused); or > 50% increase in peripheral blasts (WBC x % blasts) to > 25 x 10%/L (> 25 000/mL) (in the absence of differentiation syndrome)†; or New extramedullary disease 	In general, at least 2 cycles of flotetuzumab should be administered to determine "progressive disease". "Progressive disease" is usually accompanied by a decline in ANC and platelets, increased transfusion requirement, and decline in performance status or increase in symptoms
Recurrence/relapse	Relapse after CR is defined as a reappearance of leukemic blasts in the peripheral blood and \geq 5% blasts in the bone marrow not attributable to any other cause (e.g., bone marrow regeneration after consolidation therapy)				

CR = complete remission (includes mCR, CRc, CRm).

 $CRi = includes neutrophil count \ge 1000 \text{ or platelet count} \ge 100,000.$

*Assessment is quantitated by BM biopsy and best CBC (up to 28 days post BM biopsy).

[#] No RBC and/or platelet transfusion within 5 days prior to response assessment.

^{\$} No platelet transfusion within 5 days prior to response assessment

† Certain targeted therapies, for example, those inhibiting mutant IDH proteins, may cause a differentiation syndrome, that is, a transient increase in the percentage of bone marrow blasts and an absolute increase in blood blasts; in the setting of therapy with such compounds, an increase in blasts may not necessarily indicate PD.

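### SAP Appendix 1 allows the best CBC up to 28 days after the marrow, while SAP Section 11 and the protocol allow 14, and the primary CR/CRh endpoint is defined by Appendix 1

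*SAP*

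**What the plan says.** The SAP gives two windows for the blood count used to classify response.

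- **SAP Section 11 (Efficacy Analyses):** "Response assessment will be based on bone marrow aspirate/biopsy and the best CBC up to 14 days post bone marrow aspirate/biopsy".
- **SAP Appendix 1, asterisk footnote to the neutrophil and platelet columns:** "Assessment is quantitated by BM biopsy and best CBC (up to 28 days post BM biopsy").

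The protocol gives 14 days every time: in the synopsis (Efficacy Assessments: "the best CBC up to 14 days post bone marrow aspirate/biopsy"), in Sections 7.10 and 9.6, and in Appendix 3. The Appendix 3 footnote is the same sentence as the SAP's apart from the number: "Assessment is quantitated by BM biopsy and best CBC (up to 14 days post BM biopsy").

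SAP Section 6.1 defines the primary endpoint as "the rate of CR/CRh as assessed by the study investigators". SAP Section 11.1 adds that the investigator's classification is made "according to IWG AML response criteria (Appendix 1"). The 28-day footnote is therefore part of the criteria that the primary analysis cites.

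**The concern.** In Appendix 1, neutrophil and platelet counts, together with the transfusion conditions, separate CR and CRh from CRi and MLFS among patients whose marrow blasts are below 5%. The window decides which counts may be used. Someone who follows Section 11.1 to Appendix 1 would accept counts up to 28 days after the marrow. Someone who reads Section 11 would stop at 14. Neither document gives an order of precedence.

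The error can go only one way. The 28-day window contains the 14-day window and the best value is taken, so a patient's haematologic category can stay the same or improve.

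The study is a single-arm pivotal trial judged against fixed counts (5/40, 15/100, 25/100 and 35/170), so a few reclassified patients could change a decision. Response dates may move as well. Time to response depends on them, and so does duration of response, which "will be calculated from the time of initial documentation of response". If the window were settled after the results were known, prespecification would be weakened.

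**Working it through.** **1. The statements side by side**

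| Place | Window |
|---|---|
| Protocol synopsis, Efficacy Assessments | 14 days |
| Protocol 7.10 | 14 days |
| Protocol 9.6 | 14 days |
| Protocol Appendix 3, asterisk footnote | 14 days |
| SAP Section 11 | 14 days |
| SAP Appendix 1, asterisk footnote | 28 days |

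Five of the six agree. The exception is in the table that SAP 11.1 cites for the primary endpoint.

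**2. Which counts the difference admits**

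Both response tables place the marrow at Day 25 (+3) of a 28-day cycle. After Cycle 1:

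- The 14-day window ends at study day 25 + 14 = 39 to 28 + 14 = 42, which is Cycle 2 Day 11 to 14.
- The 28-day window ends at study day 25 + 28 = 53 to 28 + 28 = 56, which is Cycle 2 Day 25 to 28, when the next marrow is due.

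Protocol Appendix 1 schedules CBCs in later cycles on Days 1, 5, 8, 12, 15, 19, 22 and 26. On nominal days, the Day 15, 19 and 22 counts always fall outside 14 days but inside 28. Day 12 or Day 26 may do so too, depending on the day of the marrow. The data on which the two windows differ are therefore routinely collected.

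**3. Who could be affected**

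The difference matters mainly for patients with no later qualifying marrow. Protocol 7.10 can create some. At the end of Cycle 2 and later even cycles, "the bone marrow assessment may be missed if the patient has clearly not achieved CR or CRh", judged by Day 22 neutrophils below 500/µL or platelets below 50,000/µL. Take a patient with blasts below 5% after Cycle 1 who meets the CRh counts and transfusion condition on Cycle 2 Day 15 or 19 but is low on Day 22. That patient could be CRh under 28 days and not under 14, with no marrow that cycle to settle it.

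**4. The plan's own operating characteristics**

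Inputs (SAP 4.2 and 13.4): stages of 40, 60 and 70 patients; continue at ≥5/40 and ≥15/100; success at ≥25/100 or ≥35/170; H0 rate 14.7%. Let X1, X2 and X3 be binomial with n = 40, 60 and 70 and common rate p. Then

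P(success) = P(X1 ≥ 5, X1+X2 ≥ 25) + P(X1 ≥ 5, 15 ≤ X1+X2 ≤ 24, X1+X2+X3 ≥ 35).

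At p = 0.147:

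- Second interim: 0.0047 (stated 0.005).
- Final: 0.0192. Total: 0.0047 + 0.0192 = 0.0239 (stated 0.024).
- Early futility: 0.2806 + 0.2654 = 0.546 (stated 55%).

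At p = 0.23, power is 0.787 (stated as about 80%). The stated figures reproduce. The fault is in the definition and not in the arithmetic.

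**5. Illustration of sensitivity**

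The documents do not say how many patients would change category, so the shifts below are assumed.

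(a) True 14-day rate 14.7%, with k extra patients credited at the final look only. The final cut-off of 35 becomes 35 − k:

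| k | P(success) |
|---|---|
| 0 | 0.0239 |
| 1 | 0.0359 |
| 2 | 0.0531 |
| 3 | 0.0767 |

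The first step is the probability of reaching the final look with exactly 34 responders: 0.0239 + 0.0120 = 0.0359.

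(b) The wider window raises the rate at all three looks:

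| Assumed gain | p | Extra per 170 | P(success) |
|---|---|---|---|
| 0 | 0.147 | 0 | 0.0239 |
| 1 point | 0.157 | 1.7 | 0.0542 |
| 2 points | 0.167 | 3.4 | 0.1067 |
| 3 points | 0.177 | 5.1 | 0.1854 |

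**The case against.** The strongest reply is that the endpoint is the investigator's assessment. Investigators work from the protocol, which says 14 days throughout, and neither document describes the sponsor re-deriving response. Programming specifications sit in a separate statistical programming plan. On this reading the 28-day footnote never touches the primary count and is a slip in a table note. That limits the likely effect, which may be nil. It does not remove the conflict, because Section 11.1 ties the investigator's assessment to Appendix 1, and anyone checking or deriving responses from the SAP still has two windows.

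The skipped-marrow route is also narrow. It needs consultation with the Medical Monitor and a marrow result that would not affect continuation. The patient must fail on Day 22 yet qualify on another count in the gap. The Cycle 3 marrow is outside the skip rule, so a patient still on treatment can qualify then. All of this stands, and no frequency can be given.

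Finally, the illustrated probabilities do not measure this defect. The final-look-only case is artificial, since a wider window would also apply at 40 and 100 patients, and any one-patient miscount would have the same effect. That is correct. The figures show how little slack the design has and are not an estimate of type I error inflation.

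**Conclusion.** The concern holds. The SAP contradicts itself and the protocol on the CBC window that helps to define CR/CRh, and the outlying value is in the table cited for the primary endpoint. That the direction cannot be downward follows from nested windows and a best-of rule.

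The size is unknown from the documents and may be zero. It depends on whether the SAP footnote is ever applied in place of the protocol's 14 days, and on how many patients recover counts between 14 and 28 days without later qualifying at a marrow. The margin below the type I error limit is 0.025 − 0.0239 = 0.0011, so under the final-look illustration a single extra patient is enough to exceed it. The documents give no CBC window for the historical studies behind the 14.7% benchmark, so they cannot show which window makes the comparison like for like.

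This should be fixed: the contradiction is certain, its effect is uncertain, and the remedy is trivial.

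**What to change.** Before the response data are cut, change the asterisk footnote in SAP Appendix 1 from 28 to 14 days, matching SAP Section 11 and Protocol Appendix 3. Any programming specification for response should carry the same window. A sensitivity analysis using 28 days is optional.

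The cost is one SAP footnote. The protocol, sample size, boundaries, alpha and power are unchanged. The CR/CRh count can only be equal to or lower than under the 28-day window.
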